6.1.1 AEs of special interest – hepatic disorders

A thorough review of the patients who developed significant hepatotoxicity on savolitinib was undertaken. As of 30 August 2016, 387 patients/healthy volunteers have received at least 1 dose of savolitinib. Of these, 108/325 (33%) reported 303 AEs in the Hepatic Disorders SMQ. Per-patient multiple hepatic event reporting, either simultaneously or sequentially, was frequent. The most common hepatic AE was an increase in liver enzyme values (ALT, AST, ALP, or bilirubin) accounting for 221/303 events (73%), of which 22/303 (7.2%) events were serious. Overall, most liver enzyme AEs were considered by the investigator to be related to study medication (171/221 events, 77%). Most were mild or moderate in severity (171/221 events, 77%), and resolved without reduction or interruption of savolitinib (164/221 events, 74%). Fifteen of 22 serious hepatic events were considered causally related to savolitinib and 4/22 not related.

The onset of hepatic toxicity was within 1 week of exposure for 52/221, 23% of events. Over the subsequent 3 weeks, a further 110/221, 50%, events began; however, later events can develop. Ninety-five percent of events occur within the first 10 weeks. Time to resolution was up to one week in 30/303, 10%; 85/303, 28%, took between 1 and 2 weeks to resolve and 55/303, 18%, took 2 to 4 weeks to resolve. Ten patients had combined bilirubin and ALT/AST elevations consistent with potential Hy's law. Three of these patients had no other explanation for the liver biochemistry abnormalities other than liver injury caused by the savolitinib and therefore met the criteria for Hy's law. One of these 3 patients experienced a fatal event of hepatic encephalopathy and the investigator felt that there was a reasonable possibility that the event may have been caused by the savolitinib.

The hepatic adverse effect profile of savolitinib is similar to other tyrosine kinase inhibitors (TKIs), ie, a high frequency of low grade enzyme elevations and much less frequent higher-grade enzyme elevations. In general, with savolitinib, these events resolve within 2 months without dose changes. Possible confounders, the majority of which were concomitant medications with labelled hepatic adverse reactions, were of numerically limited influence, ie, reported in no more than 25% of adverse events. The hepatic event profile of savolitinib is likely to be a true drug effect, given its frequency and its consistency with other TKIs. The severity is generally low, the events are self-limiting, while being slow to resolve. Dose changes or drug discontinuation occurred in 25% of the events. On savolitinib, a rise in hepatic enzymes or bilirubin requires close monitoring until resolution, and if persistent or increasing in severity, the study medication should be interrupted or discontinued. Some patients can be successfully re-challenged at a lower dose and those with lower-grade elevations may be able to continue the drug with subsequent improvement.

Pharmacokinetic/pharmacodynamic modelling of hepatotoxicity data as of 30 June 2016 showed a link between exposure (AUC and C_{\min}) and high-grade liver elevations. Preliminary univariate extreme value modelling showed a weak-to-moderate level of evidence of a relationship between BW (body weight) and maximum LFT elevation. Patients with lower body weights may therefore be at greater risk of hepatotoxicity. A BW cut-off of 50 kg is predicted to 1) provide maximum exposures in line with the upper 90% percentile of heavier individuals, perhaps reducing hepatotoxicity risk and 2) provide minimum exposures above the minimum predicted exposure associated with the 600 mg QD dosing. Higher cut-offs may result in exposures significantly below the observed 600 mg QD exposure range. Therefore, a 400-mg dose for patients below 50 kg will be used to potentially reduce the risk of hepatotoxicity.

6.2 Definitions of serious adverse event

A serious adverse event is an AE occurring during any study phase (ie, run-in, treatment, washout, follow-up), that fulfils one or more of the following criteria:

- Results in death.
- Is immediately life-threatening.
- Requires in-patient hospitalisation or prolongation of existing hospitalisation.
- Results in persistent or significant disability or incapacity.
- Is a congenital abnormality or birth defect.
- Is an important medical event that may jeopardise the patient or may require medical intervention to prevent one of the outcomes listed above.

For further guidance on the definition of a SAE, see Appendix A to the Clinical Study Protocol.

6.3 Recording of adverse events

6.3.1 Time period for collection of adverse events

In the Part 1 screening period, only SAEs related to study procedures must be reported (AEs do not require reporting). From the signature of the main (Part 2) ICF onwards, throughout the treatment period and up to and including the 30-day follow-up period all AEs/SAEs must be reported.

6.3.2 Follow-up of unresolved adverse events

Any AE/ SAE/ abnormal laboratory findings that are ongoing at the time of study treatment discontinuation or any new treatment related events within 30 days of last study treatment, must be followed up to resolution or until the event becomes stable (or returns to baseline) or is unlikely to resolve further in the opinion of the investigator. AstraZeneca retains the right

to request additional information for any patient with ongoing AE(s)/SAE(s) at the end of the study, if judged necessary.

6.3.3 Variables

The following variables will be collect for each AE;

- AE (verbatim).
- The date and time when the AE started and stopped.
- Worst CTCAE grade and changes in grade during the course of the AE.
- Whether the AE is serious or not.
- Investigator causality rating against the Investigational Product (IP) (yes or no).
- Action taken with regard to IP.
- AE resulted in patient's withdrawal from study (yes or no).
- Outcome.

In addition, the following variables will be collected for SAEs:

- Date AE met criteria for serious AE.
- Date Investigator became aware of serious AE.
- AE is serious due to (provide all seriousness criteria applicable).
- Date of hospitalisation (if applicable).
- Date of discharge (if applicable).
- Probable cause of death (if applicable).
- Date of death (if applicable).
- Autopsy performed (if applicable).
- Causality assessment in relation to Study procedure(s).
- Causality assessment to other medication.
- Description of AE.

It is important to distinguish between serious and severe AEs. Severity is a measure of intensity whereas seriousness is defined by the criteria in Section 6.2. An AE of severe intensity need not necessarily be considered serious. For example, nausea that persists for several hours may be considered severe nausea, but not a SAE unless it meets the criteria shown in Section 6.2. On the other hand, a stroke that results in only a limited degree of disability may be considered a mild stroke but would be a SAE when it satisfies the criteria shown in Section 6.2.

The grading scales found in the National Cancer Institute (NCI) CTCAE will be utilised for all events with an assigned CTCAE grading. For those events without assigned CTCAE grades

the recommendation is that the CTCAE criteria that convert mild, moderate and severe events into CTCAE grades should be used.

A copy of the CTCAE version can be downloaded from the Cancer Therapy Evaluation program website (<http://ctep.cancer.gov>).

6.3.4 Causality collection

The investigator will assess causal relationship between Investigational Product and each Adverse Event, and answer 'yes' or 'no' to the question 'Do you consider that there is a reasonable possibility that the event may have been caused by the investigational product?'

For SAEs causal relationship will also be assessed for other medication and study procedures. Note that for SAEs that could be associated with any study procedure the causal relationship is implied as 'yes'.

A guide to the interpretation of the causality question is found in Appendix A to the Clinical Study Protocol.

6.3.5 Adverse events based on signs and symptoms

All AEs spontaneously reported by the patient during the visit or in the eDiary or reported in response to the open question from the study site staff: '*Have you had any health problems since the previous visit/you were last asked?*', or revealed by observation will be collected and recorded in the eCRF. When collecting AEs, the recording of diagnoses is preferred (when possible) to recording a list of signs and symptoms. However, if a diagnosis is known and there are other signs or symptoms that are not generally part of the diagnosis, the diagnosis and each sign or symptom will be recorded separately.

6.3.6 Adverse events based on examinations and tests

The results from the Clinical Study Protocol mandated laboratory tests and vital signs will be summarised in the CSR. Deterioration as compared to baseline in protocol-mandated laboratory values or vital signs or cardiac evaluations should therefore only be reported as AEs if they fulfil any of the SAE criteria or are the reason for discontinuation of treatment with the investigational product.

If deterioration in a laboratory value/vital sign is associated with clinical signs and symptoms, the sign or symptom will be reported as an AE and the associated laboratory result/vital sign will be considered as additional information. Wherever possible the reporting investigator uses the clinical, rather than the laboratory term (eg, anaemia versus low haemoglobin value). In the absence of clinical signs or symptoms, clinically relevant deteriorations in non-mandated parameters should be reported as AE(s).

Deterioration of a laboratory value, which is unequivocally due to disease progression, should not be reported as an AE/SAE.

Any new or aggravated clinically relevant abnormal medical finding at a physical examination as compared with the baseline assessment will be reported as an AE.

6.3.7 Hy's Law

Cases where a patient shows elevations in liver biochemistry may require further evaluation and occurrences of AST or ALT ≥ 3 xULN together with total bilirubin ≥ 2 xULN may need to be reported as SAEs. Please refer to Section 6.8.1.2 and Appendix E for further instruction on cases of increases in liver biochemistry and evaluation of Hy's Law.

6.3.8 Disease progression

Disease progression can be considered as a worsening of a patient's condition attributable to the disease for which the investigational product is being studied. It may be an increase in the severity of the disease under study (DUS) and/or increases in the symptoms of the cancer. The development of new, or progression of existing metastasis to the primary cancer under study should be considered as disease progression and not an AE. Events, which are unequivocally due to disease progression, should not be reported as an AE during the study.

6.4 Reporting of serious adverse events

All SAEs have to be reported, whether or not considered causally related to the investigational product, or to the study procedure(s). All SAEs will be recorded in the eCRF.

If any SAE occurs in the course of the study, then investigators or other site personnel inform the appropriate AstraZeneca representatives within 1 day ie, immediately but **no later than 24 hours** of when he or she becomes aware of it.

The designated AstraZeneca representative works with the investigator to ensure that all the necessary information is provided to the AstraZeneca Patient Safety data entry site **within 1 calendar day** of initial receipt for fatal and life-threatening events **and within 5 calendar days** of initial receipt for all other SAEs.

For fatal or life-threatening adverse events where important or relevant information is missing, active follow-up is undertaken immediately. Investigators or other site staff inform AstraZeneca representatives of any follow-up information on a previously reported SAE within one calendar day ie, immediately but **no later than 24 hours** of when he or she becomes aware of it.

Once the investigators or other site personnel indicate an AE is serious in the Web Based Data Capture (WBDC system), an automated email alert is sent to the designated AstraZeneca representative.

If the WBDC system is not available, then the investigator or other study site personnel reports a SAE to the appropriate AstraZeneca representative by telephone.

The AstraZeneca representative will advise the investigator/study site staff how to proceed.

The reference safety document for the definition of expectedness/listedness is Section 5.4 of the Investigator's Brochure for savolitinib and the EU Summary of Product Characteristics (SPC) for the active comparator, sunitinib.

6.5 Overdose

Overdose is defined as the accidental or intentional ingestion of any dose of investigational product that is considered both excessive and medically important. For further dosing information please refer to the IB.

- An overdose with associated AEs is recorded as the AE diagnosis/symptoms on the relevant AE modules in the eCRF and on the Overdose eCRF module.
- An overdose without associated symptoms is only reported on the Overdose eCRF module.

If an overdose on an AstraZeneca study medication occurs in the course of the study, then the investigator or other site personnel inform appropriate AstraZeneca representatives immediately, or **no later than 24 hours** of when he or she becomes aware of it.

The designated AstraZeneca representative works with the investigator to ensure that all relevant information is provided to the AstraZeneca Patient Safety data entry site.

For overdoses associated with an SAE, the standard reporting timelines apply, see Section 6.4. For other overdoses, reporting must occur within 30 days.

6.6 Pregnancy

All pregnancies occurring during the study in patients taking savolitinib, and their outcomes, should be reported to AstraZeneca except when the pregnancy is discovered before the study subject has received any study medication. Pregnancies and their outcomes in female partners of patients occurring up to 6 months after the male patient has discontinued savolitinib should be reported to AstraZeneca. Pregnancies occurring during the study in patients on sunitinib should be reported both to AstraZeneca and to Pfizer.

6.6.1 Maternal exposure

If a patient becomes pregnant during the course of the study, the study medication should be discontinued immediately.

For patients taking savolitinib, pregnancy itself is not regarded as an adverse event unless there is a suspicion that the investigational product under study may have interfered with the effectiveness of a contraceptive medication. Congenital abnormalities/birth defects and spontaneous miscarriages should be reported and handled as SAEs for patients taking savolitinib. Elective abortions without complications should not be handled as AEs. The outcome of all pregnancies (spontaneous miscarriage, elective termination, ectopic pregnancy, normal birth or congenital abnormality) should be followed up and documented even if the patient was discontinued from the study. If pregnancy occurs in patients taking sunitinib during the course of the study, adverse outcomes as listed above, should be reported as SAEs to AstraZeneca and Pfizer.

If any pregnancy occurs in patients during the course of the study, then the investigator or other site personnel informs the appropriate AstraZeneca representatives within 1 day ie, immediately but **no later than 24 hours** of when he or she becomes aware of it. The designated AstraZeneca representative works with the investigator to ensure that all relevant information is provided to the AstraZeneca Patient Safety data entry site within 1 or 5 calendar days for SAEs (see Section 6.4) and within 30 days for all other pregnancies.

The same timelines apply when outcome information is available.

6.6.2 Paternal exposure

Because studies in animals taking savolitinib have shown abnormalities in sperm development, male patients taking savolitinib should refrain from fathering a child or donating sperm during the study and for 6 months following their last dose.

Pregnancy in the partner of a patient is not considered to be an AE. However, the outcome of all pregnancies in partners of patients taking savolitinib (spontaneous miscarriage, elective termination, ectopic pregnancy, normal birth or congenital abnormality) should if possible be followed up and documented in the Pregnancy Outcome Reporting Form. Consent from the pregnant partner must be obtained (Pregnant Partner ICF) before the Pregnancy Outcome Reporting Form is completed.

6.7 Medication error

For the purposes of this clinical study a medication error is an unintended failure or mistake in the treatment process for an AstraZeneca study medication that either causes harm to the subject or has the potential to cause harm to the subject.

A medication error is not lack of efficacy of the drug, but rather a human or process related failure while the drug is in control of the study site staff or subject.

Medication error includes situations where an error:

- Occurred.
- was identified and intercepted before the subject received the drug.
- did not occur, but circumstances were recognised that could have led to an error.

Examples of events to be reported as medication errors:

- Drug name confusion.
- Dispensing error eg, medication prepared incorrectly, even if it was not actually given to the patient.
- Drug not administered as indicated, for example, wrong route or wrong site of administration.
- Drug not taken as indicated eg, tablet dissolved in water when it should be taken as a solid tablet.
- Drug not stored as instructed eg, kept in the fridge when it should be at room temperature.
- Wrong patient received the medication (excluding IVRS/IWRS errors).
- Wrong drug administered to patient (excluding IVRS/IWRS errors).

Examples of events that **do not** require reporting as medication errors in clinical studies:

- Errors related to or resulting from IVRS/IWRS - including those which lead to one of the above listed events that would otherwise have been a medication error.
- Subject accidentally missed drug dose(s) eg, forgot to take medication.
- Accidental overdose (will be captured as an overdose).
- Patient failed to return unused medication or empty packaging.
- Errors related to background and rescue medication, or standard of care medication in open label studies, even if an AZ product.

Medication errors are not regarded as AEs but AEs may occur as a consequence of the medication error.

If a medication error occurs in the course of the study, then the Investigator or other site personnel informs the appropriate AstraZeneca representatives within 1 day ie, immediately but **no later than 24 hours** of when he or she becomes aware of it.

The designated AstraZeneca representative works with the Investigator to ensure that all relevant information is completed within 1 or 5 calendar days if there is an SAE associated with the medication error (see Section 6.4) and within 30 days for all other medication errors.

6.8 Management of study medication-related toxicities - dose reductions and modifications

Toxicity will be assessed utilizing the NCI CTCAE (<https://evs.nci.nih.gov/ftp1/CTCAE/>), unless otherwise specified.

Table 8 outlines the Dose Level Reductions for each study medication. A maximum of two dose reductions will be allowed for both drugs, unless the patient has started at a savolitinib dose of 400 mg due to weight <50 kg, where only one dose reduction is allowed. No dose re-escalations are allowed. Immediate management of situations not covered by the guidelines below should be as medically indicated and with temporary suspension of study medication as appropriate, with follow up management carried out in consultation with the AstraZeneca study physician.

Table 8 Dose level reductions of study medications

Dose level	Savolitinib PO daily dose	Sunitinib PO daily dose 4 weeks on/2 weeks off
Starting dose	600 mg QD	50 mg
-1 Dose level	400 mg QD	37.5 mg
-2 Dose level	200 mg QD	25 mg

PO, Oral; QD, Once daily

6.8.1 Management of savolitinib-related toxicities

Dose modification guidelines for savolitinib study drug-related toxicities are provided in the following sections. Appropriate and optimal treatment of the toxicity is assumed prior to considering dose modifications. Prior to discontinuation of study drug due to toxicities please consult with the AstraZeneca study physician. Please see Section 6.8.1.1 for management of savolitinib-specific toxicities including dermatologic toxicity, pyrexia and hypersensitivity, Section 6.8.1.2 for hepatotoxicity management guidelines, Section 6.8.1.3 for dose modifications due to other savolitinib-related toxicity, Section 6.8.1.4 for dose modifications for savolitinib-related QTcF prolongation, and Section 6.8.1.5 for risk minimisation activities for identified and potential risks associated with savolitinib.

6.8.1.1 Guidance for management of savolitinib specific toxicities

[REDACTED]

[REDACTED]

- [REDACTED]
- [REDACTED]

[REDACTED]

[REDACTED]

6.8.1.2 Dose modification due to savolitinib-related hepatotoxicity

- Promptly evaluate patients with elevated LFTs during study treatment for alternative aetiologies and potential Hy's law criteria (ALT or AST ≥ 3 x ULN **together with** TBL ≥ 2 xULN) and discontinue potential contributing concomitant medications or alternative causal agents, as well as anti-coagulants, if appropriate.

- Ensure a PK sample is collected as soon as feasible after the patient is diagnosed with abnormal LFTs necessitating drug interruption. The date and time that the PK sample was drawn and the date and time of the last savolitinib dose prior to the PK sample must be recorded in the eCRF.

If a patient discontinues due to an LFT abnormality, LFT monitoring should continue until resolution to grade 1 or baseline or an apparent plateau has been reached.

- 1 Discontinue savolitinib if
 - ALT or AST >8x ULN, or
 - ALT or AST >5x ULN for >2 weeks, or
 - ALT or AST >3x ULN and (TBL>2x ULN or INR>1.5 if not on anticoagulants that elevate the INR).
 - AST or ALT >3x ULN with the appearance of fatigue, nausea, vomiting, right upper quadrant pain or tenderness, fever, rash, and/or eosinophilia >5%
- 2 Withhold savolitinib if ALT or AST >5-8x ULN without TBL elevation above baseline or ULN, repeat LFT testing twice a week for 1 week;
 - If improved to grade 1 or baseline in 1 week, resume at reduced dose with LFT testing twice a week for 6 weeks;
 - If not, discontinue
- 3 Withhold savolitinib if ALT or AST >3x ULN and concurrent TBL 1.5~2x ULN, repeat LFT testing twice a week for 1 week,
 - If both ALT/AST and TBL improve to grade 1 or baseline in 1 week, resume at reduced dose with LFT testing twice a week for 6 weeks
 - If not, discontinue
- 4 Continue savolitinib if ALT or AST >3-5x ULN without TBL elevation above baseline or ULN, repeat LFT testing every week
 - If ALT or AST are trending upward, withhold dosing and repeat LFT twice a week for 1 week;
 - if improved to grade 1 or baseline in 1 week, resume at same dose with LFT testing every week for 6 weeks
 - if improved to grade 1 or baseline in 2 weeks, resume at reduced dose with LFT testing every week for 6 weeks
 - If not, discontinue
- 5 Discontinue savolitinib for recurrent Grade 3 ALT or AST (>5x ULN)
- 6 Discontinue savolitinib for recurrent Grade 2 ALT or AST (>3-5x ULN) and TBL >1.5~2x ULN
- 7 Withhold savolitinib for recurrent Grade 2 ALT or AST >3-5x ULN without TBL elevation above baseline or ULN, repeat LFT testing twice a week for 1 week
 - if improved to grade 1 or baseline in 1 week, resume at reduced dose with LFT testing every week for 6 weeks;

- if not, discontinue savolitinib.

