Appendix E Actions Required in Cases of Increases in Liver Biochemistry and Evaluation of Hy's Law

Introduction

This Appendix describes the process to be followed in order to identify and appropriately report potential Hy's Law (PHL) cases and Hy's Law (HL) cases. It is not intended to be a comprehensive guide to the management of elevated liver biochemistries. Specific guidance on the management of liver abnormalities can be found in Section 6.8.1.2 of the protocol.

During the course of the study the Investigator will remain vigilant for increases in liver biochemistry. The investigator is responsible for determining whether a patient meets PHL criteria at any point during the study.

All sources of laboratory data are appropriate for the determination of PHL and HL events. These include samples taken at scheduled study visits and other visits including central and all local laboratory evaluations, even if collected outside of the study visits. For example, PHL criteria could be met by an elevated ALT from a central laboratory **and/or** elevated TBL from a local laboratory.

The Investigator will also review adverse event (AE) data (for example, for AEs that may indicate elevations in liver biochemistry) for possible PHL events.

The Investigator will participate, together with AstraZeneca clinical project representatives, in review and assessment of cases meeting PHL criteria to agree whether HL criteria are met. HL criteria are met if there is no alternative explanation for the elevations in liver biochemistry other than Drug Induced Liver Injury (DILI) caused by the Investigational Medicinal Product (IMP).

The Investigator is responsible for recording data pertaining to PHL/HL cases and for reporting AEs and Serious Adverse Events (SAEs) according to the outcome of the review and assessment in line with standard safety reporting processes.

Definitions

Potential Hy's Law (PHL)

Aspartate Aminotransferase (AST) or Alanine Aminotransferase (ALT) $\geq 3x$ Upper Limit of Normal (ULN) **together with** Total Bilirubin (TBL) $\geq 2x$ ULN at any point during the study following the start of study medication irrespective of an increase in Alkaline Phosphatase (ALP).

Hy's Law (HL)

AST or ALT $\geq 3xULN$ **together with** TBL $\geq 2xULN$, where no other reason, other than the IMP, can be found to explain the combination of increases, eg, elevated ALP indicating cholestasis, viral hepatitis, another drug.

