For PHL and HL the elevation in transaminases must precede or be coincident with (ie, on the same day) the elevation in TBL, but there is no specified timeframe within which the elevations in transaminases and TBL must occur.

Identification of potential Hy's Law cases

In order to identify cases of PHL it is important to perform a comprehensive review of laboratory data for any patient who meets any of the following identification criteria in isolation or in combination:

- ALT $\geq 3xULN$
- AST $\geq 3xULN$
- TBL $\geq 2xULN$

The Investigator will without delay review each new laboratory report and if the identification criteria are met will:

- Notify the AstraZeneca representative.
- Determine whether the patient meets PHL criteria (see Definitions within this Appendix for definition) by reviewing laboratory reports from all previous visits.
- Promptly enter the laboratory data into the laboratory eCRF.

Follow-up:

Potential Hy's Law criteria not met

If the patient does not meet PHL criteria the Investigator will:

- Inform the AstraZeneca representative that the patient has not met PHL criteria.
- Perform follow-up on subsequent laboratory results according to the guidance provided in the Clinical Study Protocol.

Potential Hy's Law criteria met

If the patient does meet PHL criteria the Investigator will:

- Notify the AstraZeneca representative who will then inform the central Study Team.

- Within 1 day of PHL criteria being met, the Investigator will report the case as an SAE of PHL; serious criteria 'Important medical event' and causality assessment 'yes/related' according to CSP process for SAE reporting.
- For patients that met PHL criteria prior to starting IMP, the Investigator is not required to submit a PHL SAE unless there is a significant change* in the patient's condition.

The AstraZeneca Study Physician contacts the Investigator, to provide guidance, discuss and agree an approach for the study patients' follow-up (including any further laboratory testing) and the continuous review of data. Subsequent to this contact the Investigator will:

- Monitor the patient until liver biochemistry parameters and appropriate clinical symptoms and signs return to normal or baseline levels, or as long as medically indicated.
- Complete the follow-up SAE form as required.
- Investigate the aetiology of the event and perform diagnostic investigations as discussed with the AstraZeneca Study Physician.

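### Section 6.8.1.2 has no liver rule for bilirubin above ULN and baseline but below 1.5x ULN, so two holds that are mandatory with normal bilirubin become discretionary when it is mildly raised

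*Protocol*

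**What the plan says.** Protocol section 6.8.1.2 sets seven numbered items for savolitinib. Three apply only when bilirubin is not raised:

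- Item 2: "Withhold savolitinib if ALT or AST >5-8x ULN without TBL elevation above baseline or ULN". The patient resumes at a reduced dose if recovered to grade 1 or baseline within 1 week, and otherwise stops.
- Item 4: "Continue savolitinib if ALT or AST >3-5x ULN without TBL elevation above baseline or ULN". LFTs are weekly. If values rise, dosing is held, with up to 2 weeks to recover.
- Item 7: "Withhold savolitinib for recurrent Grade 2 ALT or AST >3-5x ULN without TBL elevation above baseline or ULN". The deadline is 1 week, with resumption at a reduced dose or discontinuation.

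The items for raised bilirubin start higher. Item 3 reads "Withhold savolitinib if ALT or AST >3x ULN and concurrent TBL 1.5~2x ULN". Item 6 (stop on a recurrent >3-5x ULN) needs TBL above 1.5x ULN, and the bilirubin arm of item 1 needs TBL above 2x ULN.

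Some stops ignore bilirubin. In item 1 these are ALT/AST >8x ULN, "ALT or AST >5x ULN for >2 weeks", >3x ULN with INR above 1.5, and >3x ULN with listed symptoms or eosinophilia. Item 5 stops any recurrent >5x ULN.

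Section 6.8 leaves situations outside the guidelines to medical judgement, with suspension as appropriate and follow-up management in consultation with the study physician. Sections 1.3 and 6.8.1.5 say that the algorithm clearly defines and limits who may be re-challenged.

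**The concern.** The bilirubin conditions do not meet. Items 2, 4 and 7 end at ULN or baseline, and items 3 and 6 begin at 1.5x ULN. A patient between those limits can have a substantial transaminase rise with no item saying whether to hold, continue or resume.

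A rule of this kind should not become weaker as bilirubin worsens, yet in part of the band it does. Liver injury is savolitinib's adverse event of special interest. Section 6.1.1 reports ten potential Hy's law cases, three of which met the criteria, and one of those three was fatal. At stake are the consistency of dose handling across sites and the accuracy of the statement that re-challenge is clearly defined.

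**Working it through.** No plan figure needs to be reproduced. The check applies each item of section 6.8.1.2 in turn.

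**Inputs.** ALT/AST >3-5x or >5-8x ULN; first or recurrent; duration up to 2 weeks or longer; TBL in four bands. The patient is asymptomatic, without eosinophilia, and INR is at or below 1.5.

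**Main grid, duration up to 2 weeks.** Where a recurrence item and a general item both apply, the recurrence item is shown.

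| ALT/AST | TBL normal | TBL above ULN and baseline, <1.5x | TBL 1.5-2x | TBL >2x |
|---|---|---|---|---|
| First >3-5x | 4: continue | none | 3: hold | 1: stop |
| First >5-8x | 2: hold | none | 3: hold | 1: stop |
| Recurrent >3-5x | 7: hold | none | 6: stop | 1: stop |
| Recurrent >5-8x | 5: stop | 5: stop | 5: stop | 1 and 5: stop |

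**Within the band, adding duration.** There are 2 ALT/AST levels x 2 (first or recurrent) x 2 durations = 8 combinations. Three meet a stop: recurrent >5-8x at both durations (item 5), and first >5-8x beyond 2 weeks (item 1). The other 8 - 3 = 5 meet no item: first >3-5x at both durations, recurrent >3-5x at both durations, and first >5-8x up to 2 weeks. These are three clinical situations. The count is of rule combinations, not patients.

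**Dependence on wording.** The shared bilirubin condition can mean below either limit or below both. With ALT 6.5x, TBL 1.2x and baseline 0.8x, no item applies under either reading. With baseline 1.3x, which inclusion criterion 9 allows if ALT and AST are normal, no item applies only under the below-both reading. Limiting the point to TBL above both limits therefore makes it independent of the reading.

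**Direction of the rule.**
- First >5-8x: a hold is required on both sides of the gap (items 2 and 3).
- Recurrent >3-5x: a hold on the lower side (item 7) and a stop on the upper side (item 6).
- First >3-5x: continue on the lower side (item 4) and hold on the upper side (item 3). No mandatory initial hold is lost here, so this is a gap but not an inversion.

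**Example.** A first asymptomatic ALT of 6x ULN, with normal baseline, falls to 4x after a week. With normal TBL, item 2 requires a hold and then discontinuation, because the protocol itself labels >3-5x as grade 2 and grade 1 was not reached. With TBL 1.2x, no item requires a hold at 6x and none applies at 4x, because item 1's two-week stop counts only time above 5x.

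**Comparator.** Table 11 for sunitinib covers hepatic toxicity and holds at grade 3 with no bilirubin condition. Item 5 equates grade 3 with >5x ULN. At ALT 6x and TBL 1.2x sunitinib must be held, while no savolitinib item requires it.

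**Exposure.** About 50 patients randomised 1:1 gives 50 / 2 = about 25 on savolitinib.

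**The case against.** The strongest reply is that the fallback works. Section 6.8 brings in the study physician. Section 6.1.1 asks for close monitoring until resolution, and for interruption or discontinuation if values persist or worsen. Appendix E requires prompt review and sponsor notification from ALT or AST 3x ULN. Sections 1.3 and 6.8.1.5 limit re-challenge to lower-grade abnormalities with rapid resolution.

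This stands to an extent. A reader might infer that the protocol permits dosing to continue at ALT 6x with TBL 1.2x. It does not: the comparison is between a mandatory rule and supervised discretion. But none of these texts sets a hold threshold, a recovery deadline or a resumption dose. Appendix E says of itself "It is not intended to be a comprehensive guide to the management of elevated liver biochemistries" and refers back to 6.8.1.2.

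The second reply concerns the remedy. It is tempting to extend item 3 down over the whole band and call the cost a 1-week hold. The documents do not support that for a first >3-5x ULN. Item 3 ends in permanent discontinuation if recovery is not reached in 1 week. Section 6.1.1 reports resolution within a week for 30/303 hepatic events (10%), with 85/303 (28%) taking 1 to 2 weeks and 55/303 (18%) taking 2 to 4 weeks. Improvement to grade 1 is easier than resolution, so 10% is not the pass rate, but discontinuation is foreseeable. The same section says that 164/221 liver-enzyme events (74%) resolved without reduction or interruption. This objection stands in full for that situation.

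Third, the uncovered patient is narrowly defined. Nausea, vomiting or fatigue appearing at >3x ULN already forces a stop under item 1, and these are common with savolitinib (41.6%, 24.0% and 21.0% as related events in section 1.1.3.4). That supports a low rating but does not close the gap.

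**Conclusion.** The gap holds on the face of section 6.8.1.2. In the stated band, three situations have no item. In two of them, first >5-8x ULN up to 2 weeks and recurrent >3-5x ULN, the rule is inverted: worse bilirubin turns a mandatory hold into a discretionary one. For this band the claim in sections 1.3 and 6.8.1.5 that re-challenge is clearly defined is not met.

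Severity is minor. About 25 patients receive savolitinib, recruitment is closed apart from patients already in screening, and 95% of hepatic events fall within the first 10 weeks. The number who would enter the band cannot be derived from the protocol. A reader might link the fatal case or the other Hy's law cases to this gap, but the protocol does not say whether any of them passed through it.

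The conclusion assumes no listed symptoms or eosinophilia, INR at or below 1.5, and TBL above both limits.

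**What to change.** Edit two items in section 6.8.1.2.

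1. Item 2: replace the bilirubin condition with *with TBL below 1.5x ULN*. Keep the hold, the 1-week deadline and reduced-dose resumption. It then meets item 3.
2. Item 7: replace the same condition with *with TBL up to and including 1.5x ULN*. Keep the hold and the 1-week deadline. It then meets item 6. At exactly 1.5x ULN item 3 also applies to a recurrence, but both items require a hold and a reduced dose.

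In both items, if TBL was above baseline and ULN, require it to return to baseline or to ULN or below before dosing resumes. A grade 1 bilirubin test would add little. Item 3 starts at 1.5x ULN and accepts grade 1 as recovery, so the protocol appears to treat this band as grade 1 already.

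For a first >3-5x ULN in the band, the sponsor should state which neighbour applies. Item 4 means continuing with weekly LFTs and up to 2 weeks to recover if held. Item 3 means a hold with a 1-week deadline. This is a clinical trade-off that the documents do not settle.

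The cost is an amendment to two items, one added sentence and a site memo, with no new test or visit type. An occasional patient would have a mandatory hold, and permanent discontinuation if recovery is not reached in 1 week, as items 2, 3 and 7 already require.
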